This is a multi-center one-stage phase II trial conducted at UAB Comprehensive Cancer Center and outside sites, and managed by the CTNMO (Clinical Trial Network Monitoring Office) housed at the UAB Comprehensive Cancer Center. Clinical PFS as the primary end-point and the trial will enroll 28 patients. The eligible population includes men with metastatic castration-resistant prostate cancer (CRPC) who have received prior abiraterone and/or enzalutamide (prior chemotherapy is allowed). Carfilzomib is administered twice-weekly on consecutive days (± 1 day) (days 1, 2, 8, 9, 15, 16) as a 30 minute intravenous (IV) infusion for 3 weeks every 4 weeks (1 cycle) with dexamethasone and acetaminophen premedication as well as normal saline 250 ml over 30 minutes as pre-hydration. The dose of carfilzomib is 20 mg/m² on days 1 and 2 of cycle 1 and then escalated in succeeding weeks and cycles to 56 mg/m² for no dose limiting toxicities (DLTs) occur defined as any grade ≥ 3 non-hematologic toxicity or grade ≥ 4 neutropenia or thrombocytopenia lasting ≥ 7 days.

Acyclovir 400 mg orally twice daily is required during therapy, which may be discontinued ≥ 7 days after the last dose of carfilzomib. Therapy will continue until progression (as defined below) or severe toxicities. Patients removed from the trial for toxicities or other reasons will continue to be followed until progression or starting a new agent. Androgen deprivation therapy with LHRH analogue or antagonist and bone protecting agent (denosumab or zoledronic acid) will also continue. Comprehensive metabolic panel (CMP) evaluations are performed on day 1 every 4 weeks, complete blood cell (CBC) counts on days 1, 8 and 15 every cycle, and radiological evaluations are performed every 3 cycles or earlier if clinically indicated. Pain (PPI score, Appendix B) and analgesic intake (Appendix C) are recorded on day 1 of every cycle. Correlative studies include serial CTC enumeration (repeated on day 1 cycle 2 and day 1 cycle 4) and collection of whole blood is performed at baseline for 20S proteasome activity. Progression of disease will be defined clinically as the first occurrence of any of the following, and PSA progression alone will not constitute progression:

- 1) Two distinct new lesions on bone scan consistent with bone metastases in the best judgment of the investigator and confirmed by further new lesions on a subsequent scan ≥ 6 weeks later.

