18. Has a serious uncontrolled intercurrent medical or psychiatric illness, including serious infection
19. Is unable to comply with study requirements
20. Uncontrolled intercurrent illness including, but not limited to, ongoing or active infection, symptomatic congestive heart failure, unstable angina pectoris, cardiac arrhythmia, or psychiatric illness/social situations that would limit compliance with study requirements.

STUDY CALENDAR

Baseline evaluations are to be conducted within 2 weeks prior to administration of protocol therapy. Scans and x-rays must be done ≤ 4 weeks prior to the start of therapy. In the event that the patient's condition is deteriorating, laboratory evaluations should be repeated within 48 hours prior to initiation of the next cycle of therapy.

	-28 days	-14 days (may serve as cycle 1 day 1 labs)	Day 1 (± 1 day) of every cycle (28 days)	Day 8 and 15 every cycle (± 1 day)	Day 1 Every 3 cycles	30 (± 7 days) post last treatment
ASSESSMENTS						
History and exam (H&P)	X		X			X ¹
ECOG performance status		X	X			X ¹
CBC with differential		X	X	X		X ¹
CMP		X	X			X ¹
PSA		X	X			X ¹
LDH		X				
Testosterone level		X				
Pain (PPI 0-5 scale)		X	X			X ¹
Analgesic intake (increased, decreased or stable)		X	X			X ¹
Echocardiogram	X		X ^{6,7}			
DISEASE ASSESSMENT						
CT chest, abdomen, pelvis	X				X	X ¹
Bone Scan	X				X	X ¹
TREATMENT						
Carfilzomib day 1,2, 8,9,15,16 (30 min IV infusion)			X ²	X ²		
Premedication (Dexamethasone, Acetaminophen)			X ³	X ³		
Pre-hydration (Normal saline 250-500 ml over 30 minutes)			X ⁴	X ⁴		
Acyclovir 400 mg PO bid			X ⁵	X ⁵		
LHRH analogue (if no prior orchiectomy)					X	
CORRELATIVE STUDIES						
CTC enumeration (3 time points)	X		X (cycle 2)		X (cycle 4)	

			only)		only)	
Whole Blood 20S proteasome assay	X					
FOLLOW-UP						
Disease progression and survival						X ¹

¹Patients removed from trial for reasons other than progression will continue to be followed until progression or initiation of new therapy (whichever comes first); i.e. H&P, laboratory evaluation, pain, analgesic intake are performed every ~28 days and radiographic evaluation every ~90 days (+/-7 days)

²Dose is 20 mg/m² on days 1, 2 of cycle 1 and if no DLTs, escalate to 56 mg/m² for all remaining doses, Subjects with a Body Surface Area (BSA) > 2.2 m² will receive a capped dose of 44 mg of carfilzomib (at the 20 mg/m² dose level) or 123 mg of carfilzomib (at the 56 mg/m² dose level).

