6.3 Duration of Therapy

Therapy will continue until progression (as defined below) or severe toxicities. Acyclovir will continue from day 1 of cycle 1 until ≥7 days after the last dose of carfilzomib. Androgen deprivation therapy with LHRH analogue or antagonist and bone protecting agent (denosumab or zoledronic acid) will also continue. If the bone protective agent has not already been initiated ≥4 weeks before trial registration, initiation of a bone protection agent is not allowed. CMP evaluations are performed on day 1 every 4 weeks,

CBC on days 1, 8 and 15 every cycle, and radiological evaluations are performed every 3 cycles or earlier if clinically indicated. Correlative studies include serial CTC enumeration (repeated on day 1 cycle 2, then q 3 cycles) and collection of whole blood is performed at baseline for 20S proteasome activity and other potential future correlative studies.

Progression of disease will be defined clinically as the first occurrence of any of the following and PSA progression alone will not constitute progression.

- 1) Two distinct new lesions on bone scan consistent with bone metastases in the best judgment of the investigator and confirmed by further new lesions on a subsequent scan ≥ 6 weeks later.
- 2) Progression in measurable disease as defined by RECIST criteria
- 3) Worsening of pain in the judgment of the investigator.
- 4) New bladder outlet or ureteral obstruction caused by cancer
- 5) New bone related events
 - a. Pathologic fracture
 - b. Spinal cord compression
 - c. Need for palliative radiation, surgery, or kyphoplasty to any neoplastic bone lesion
- 6) Deterioration of performance status to ECOG level 3-4
- 7) Death

Therapy is also discontinued for other non-progression events below:

- 1) Intercurrent illness that prevents further administration of treatment
- 2) Unacceptable adverse event(s)
- 3) Patient decides to withdraw from the study
- 4) General or specific changes in the patient's condition render the patient unacceptable for further treatment in the judgment of the investigator.

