7. DOSING DELAYS/DOSE MODIFICATIONS/SAFETY CONSIDERATIONS

According to design of drug administration, patients not experiencing DLTs in the first week of the first cycle with 20 mg/m² (defined as any grade ≥ 3 non-hematologic toxicity (except grade ≥ 2 neurotoxicity), or grade ≥ 4 neutropenia or thrombocytopenia lasting ≥ 7 days) will undergo dose escalation from the second week to 56 mg/m². Before each drug dose, the patient will be evaluated for possible toxicities that may have occurred after the

previous dose(s). Toxicities are to be assessed according to the NCI Common Terminology Criteria for Adverse Events (CTCAE), Version 4.03 (Appendix D).

Carfilzomib is to be restarted at the same schedule the patient was on before therapy was held, and the dose must be reduced for toxicities as follows:

- If the patient was receiving 56 mg/m², reduce the dose to 45 mg/m².
- If the patient was receiving 45 mg/m², reduce the dose to 36 mg/m².
- If the patient was receiving 36 mg/m², reduce the dose to 20 mg/m².
- If the patient was receiving 20 mg/m², reduce the dose to 15 mg/m².

Dose reductions for Hematologic Toxicities

Study drug will be withheld from subjects with:

- Grade 4 lymphopenia persisting for > 14 days, if lymphopenia was not pre-existing
- Grade 4 thrombocytopenia with active bleeding
- Grade 4 anemia and thrombocytopenia requires the carfilzomib dose to be withheld. Subjects should receive supportive measures in accordance with institutional guidelines.

The following table outlines the dose reduction guidelines for carfilzomib for thrombocytopenia and neutropenia:

Thrombocytopenia	
	Recommended Action
When Platelets:	Carfilzomib
Fall to < 30 × 10 ⁹ /L	Interrupt carfilzomib, follow CBC weekly
Return to ≥ 30 × 10 ⁹ /L	Resume at full dose
Subsequently drop to < 30 × 10 ⁹ /L	Interrupt carfilzomib, follow CBC weekly
Return to ≥ 30 × 10 ⁹ /L	Resume at 1 dose decrement

Neutropenia	
	Recommended Action
When ANC	Carfilzomib
Falls to < 0.5 × 10 ⁹ /L	Interrupt carfilzomib add filgrastim per ASCO guidelines if Gr ≥3 with fever, follow CBC weekly
Returns to > 1.0 × 10 ⁹ /L (if neutropenia was the only toxicity noted)	Resume at full dose

Returns to $> 1.0 \times 10^9/L$ (if other toxicity noted)	Resume at 1 dose decrement
Subsequently drops to $< 0.5 \times 10^9/L$	Interrupt carfilzomib
Returns to $> 1.0 \times 10^9/L$	Resume at 1 dose decrement

Dose Reductions for Non-Hematologic Toxicities

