Dose adjustments do not need to be made for weight gains/losses of $\leq 20\%$. Subjects with a Body Surface Area (BSA) $> 2.2 \text{ m}^2$ will receive a capped dose of 44 mg of carfilzomib (at the 20 mg/m^2 dose level) or 123 mg of carfilzomib (at the 56 mg/m^2 dose level).

Safety Considerations

Based upon the experience in the Phase 1 and 2 clinical studies with carfilzomib, the following observations are noted:

- A “first dose effect” has been seen, which is notable for fever, chills, rigors, and/or dyspnea occurring during the evening following the first day of infusion and an increase in creatinine on Day 2, which may be the clinical sequelae of rapid tumor lysis and/or cytokine release.
- Should a “first dose” effect occur at any point during Cycle 1 or 2, treatment with high dose glucocorticoids (e.g. methylprednisolone 50–100 mg) is recommended. In addition, intravenous fluids, vasopressors, oxygen, bronchodilators, and acetaminophen should be available for immediate use and instituted, as medically indicated.
- Dexamethasone 4 mg PO/IV will be administered prior to all carfilzomib doses during the 1st cycle and prior to all carfilzomib doses during the first dose-escalation (56 mg/m^2) cycle. If treatment-related fever, rigors, chills, and/or dyspnea are observed post any dose of carfilzomib after dexamethasone has been discontinued, dexamethasone (4 mg PO/IV) should be re-started and administered prior to subsequent doses.
- Acyclovir or similar should be given to all subjects unless contraindicated.

- CrCl changes are mostly transient, reversible, and non-cumulative. All subjects should be well hydrated. Clinically significant electrolyte abnormalities should be corrected prior to dosing with carfilzomib. Renal function must be monitored closely during treatment with carfilzomib. Serum chemistry values, including creatinine, must be obtained and reviewed prior to each dose of carfilzomib during Cycles 1 and 2. Carfilzomib must be held for subjects with a CrCl < 15 mL/min at any time during study participation as outlined.
- Subjects with active or suspected infection of any kind that required systemic treatment should not be dosed with carfilzomib until the infection has resolved and if being treated with anti-infective, the course of antibiotics has been completed.

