8. STUDY CALENDAR

Baseline evaluations are to be conducted within 2 weeks prior to administration of protocol therapy. Scans and x-rays must be done ≤4 weeks prior to the start of therapy. In the event that the patient's condition is deteriorating, laboratory evaluations should be repeated within 48 hours prior to initiation of the next cycle of therapy.

	-28 days	-14 days (may serve as cycle 1 day 1 labs)	Day 1 (± 1 day) of every cycle (28 days)	Day 8 and 15 every cycle (± 1 day)	Day 1 Every 3 cycles	30 (± 7 days) post last treatment
ASSESSMENTS						
History and exam (H&P)	X		X			X ¹
ECOG performance status		X	X			X ¹
CBC with differential		X	X	X		X ¹
CMP		X	X			X ¹
PSA		X	X			X ¹
LDH		X				
Testosterone level		X				
Pain (PPI 0-5 scale)		X	X			X ¹
Analgesic intake (increased, decreased or stable)		X	X			X ¹
Echocardiogram	X		X ^{6,7}			
DISEASE ASSESSMENT						

CT chest , abdomen, pelvis	X				X	X ¹
Bone Scan	X				X	X ¹
TREATMENT						
Carfilzomib day 1,2, 8,9,15,16 (30 min IV infusion)			X ²	X ²		
Premedication (Dexamethasone, Acetaminophen)			X ³	X ³		
Pre-hydration (Normal saline 250-500 ml over 30 minutes)			X ⁴	X ⁴		
Acyclovir 400 mg PO bid			X ⁵	X ⁵		
LHRH analogue (if no prior orchiectomy)					X	
CORRELATIVE STUDIES						
CTC enumeration (3 time points)	X		X (cycle 2 only)		X (cycle 4 only)	
Whole Blood 20S proteasome assay	X					
FOLLOW-UP						
Disease progression and survival						X ¹

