All other SAE's will be sent to Onyx on a biannual basis in the form of a line listing in English. The line listing must include the following information; patient initials, date of birth, sex, SAE onset date, SAE stop date, event name (term), outcome, date of first dose of study drug(s), date of last dose of study drug(s) prior to the event, action taken with study drug(s) the Investigator's assessment of causality (relationship to carfilzomib), and the Investigator's assessment of expectedness to carfilzomib. The sponsor reserves the right to review the CRFs or source documents in response to any inquiries by regulatory agencies that the sponsor may receive.

Onyx Drug Safety and Pharmacovigilance Contact Information:

Drug Safety Reporting Email: [contact]

Drug Safety Reporting [contact] (toll fax) or 1 [contact] (US toll-free fax)

Pregnancy Reporting by Investigator-sponsor to Onyx

If a subject or partner of a subject becomes pregnant during treatment with an Onyx product(s) or up to 30 days following the last dose of an Onyx product(s), the Investigator-sponsor will notify Onyx within 24 hours of learning of the pregnancy. The investigator will complete a local Pregnancy Monitoring Form and report the information regarding the pregnancy, outcome, and status of the newborn, to Onyx via the contact information above as appropriate.

If the subject becomes pregnant while taking an Onyx product(s), the drug will be immediately discontinued. The investigator will discuss the risks and concerns of investigational drug exposure to a developing fetus and counsel the subject and/or pregnant partner (or ensure that such counseling is provided). Pregnancies will be followed through the outcome of the pregnancy. Newborns should be followed for a minimum of 12 weeks.

Routine Adverse Event Reporting

All Adverse Events **must** be reported in routine study data submissions. AEs reported must also be reported in routine study data submissions. Safety will be monitored throughout the study by physical examinations, review of adverse events (AEs), and laboratory studies. The frequency of safety monitoring procedures is outlined in Section 7. Criteria that will be used throughout the study for dose interruption, reduction, and discontinuation of chemotherapeutic agents are specified in Section 7. The frequency of efficacy monitoring and procedures are outlined in Sections 8.

Data and Safety Monitoring Plan

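### Ten of the 12 pre-dose creatinine checks that Section 7 requires in cycles 1 and 2 are not on the printed schedule; separately, dexamethasone with 56 mg/m² is given as both 8 mg and 4 mg

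*Combined protocol and SAP*

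**What the plan says.** **Chemistry.** Section 7, Safety Considerations: "Serum chemistry values, including creatinine, must be obtained and reviewed prior to each dose of carfilzomib during Cycles 1 and 2". Section 6.1 sets six infusions per cycle, on days 1, 2, 8, 9, 15 and 16.

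The scheduling text is different. The synopsis (Trial Design) and Section 3.1 both say of the comprehensive metabolic panel (CMP) that "evaluations are performed on day 1 every 4 weeks, complete blood cell (CBC) counts on days 1, 8 and 15 every cycle". Section 6.3 repeats it: "CMP evaluations are performed on day 1 every 4 weeks". In both calendars (synopsis and Section 8), CMP is marked at screening, on day 1 of each cycle and 30 days after the last treatment. The day 8/15 column is blank for CMP but marked for CBC. No footnote adds pre-dose chemistry. The heading of the screening laboratory column reads in part "14 days (may serve as cycle 1 day 1 labs".

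Section 9 says: "The frequency of safety monitoring procedures is outlined in Section 7".

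**Dexamethasone.** Section 6.1 and footnote 3 of both calendars give 4 mg with carfilzomib 20 mg/m² and 8 mg with 56 mg/m². Section 7 gives 4 mg before every dose of cycle 1 and of the first dose-escalation cycle. It says so under Safety Considerations, which labels the escalation cycle as 56 mg/m², and again under Required Concomitant Medications. Section 7 also says that patients without a dose-limiting toxicity in week 1 "will undergo dose escalation from the second week to 56 mg/m²".

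**The concern.** A site that orders laboratory tests from the calendar would not meet Section 7, although Section 7's wording is mandatory. Three dosing rules in Section 7 need a current chemistry:

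- the hold for creatinine clearance below 30 mL/min;
- the tumor lysis hold, defined by changes in creatinine, uric acid, phosphate, potassium, calcium or LDH;
- the week 2 escalation, allowed only if week 1 had no dose-limiting toxicity, which includes any grade 3 or higher non-hematologic toxicity.

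Two of the uncovered days matter most. Section 7 describes a first-dose effect with a creatinine rise on day 2. Cycle 1 day 8 is the step from 20 to 56 mg/m². The printed schedule has no chemistry on either day.

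The dexamethasone texts conflict outright. Escalation starts on cycle 1 day 8, so on days 8, 9, 15 and 16 of cycle 1 a site cannot follow both Section 6.1 and Section 7.

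**Working it through.** The plan states no figure to reproduce here, and no power or alpha calculation is involved. The check is a count.

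**1. Chemistry in cycles 1 and 2** (dosing days from Section 6.1, requirement from Section 7, schedule from the synopsis, Sections 3.1, 6.3 and 8)

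| Days | Doses (days × 2 cycles) | Chemistry required | CMP scheduled | CBC scheduled |
|---|---|---|---|---|
| 1 | 1 × 2 = 2 | 2 | 2 | 2 |
| 8, 15 | 2 × 2 = 4 | 4 | 0 | 4 |
| 2, 9, 16 | 3 × 2 = 6 | 6 | 0 | 0 |
| Total | 12 | 12 | 2 | 6 |

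Unscheduled: 12 − 2 = 10, or 6 − 1 = 5 per cycle. Four of the 10 fall on days when a CBC is already drawn, and all 10 fall on infusion days. Two is the most the schedule covers, because the screening sample, up to 14 days old, may stand in for cycle 1 day 1.

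For 28 patients, the total is 28 × 5 = 140 if all receive a full cycle 1 and none starts cycle 2, and 28 × 10 = 280 if all complete both cycles. Patients who stop during cycle 1, or miss doses, would reduce these totals.

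**2. Does other text fill the gap?** Section 7 also says "Before each drug dose, the patient will be evaluated for possible toxicities", but names no laboratory test. The calendar preamble says "laboratory evaluations should be repeated within 48 hours prior to initiation of the next cycle of therapy", but only for a deteriorating patient and only before a new cycle. Neither supplies a sample on days 2, 8, 9, 15 or 16.

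**3. Dexamethasone in cycle 1, patient escalated on day 8**

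- Section 6.1 and calendar footnotes: 2 × 4 mg + 4 × 8 mg = 40 mg.
- Section 7: 6 × 4 mg = 24 mg.
- Difference: 40 − 24 = 16 mg, from four doses (days 8, 9, 15, 16).

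The 8 mg rule stands in three places and the 4 mg rule in two. The 4 mg rule cannot be read as limited to 20 mg/m², since Safety Considerations applies it to the 56 mg/m² cycle by name. The option to stop dexamethasone opens only from cycle 2, so it does not remove the cycle 1 conflict.

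**The case against.** The best defence on chemistry is that nothing conflicts. Section 9 makes Section 7 the source for safety-monitoring frequency, and a routine day 1 panel does not forbid further samples, so a site can comply with every sentence. That is right as far as it goes: the 10 checks are required and simply not shown. It does not excuse five scheduling locations that omit them.

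The renal risk also looks modest in the plan's own account. Section 7 calls creatinine clearance changes mostly transient, Section 1.3 says dose adjustment for renal dysfunction appears unnecessary, Section 7 reports similar adverse events across renal groups, and clearance below 30 mL/min is excluded at entry. Oversight is frequent: weekly committee discussion of each subject (Section 14), weekly monitoring of adverse reactions at UAB (Section 9), and monthly off-site source review of all network patients (Section 14). These points limit the severity. The weekly meetings could stop an omission from being repeated, but none of these reviews takes place before a dose. How sites build their visit orders is not described, so the number of samples that would actually be missed is unknown.

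Two further points stand without changing the conclusion. Section 7 also states a hold at clearance below 15 mL/min, which is not reconciled with the 30 mL/min hold; either threshold needs a current creatinine. The tumor lysis rule also uses LDH, uric acid and phosphate, which a chemistry footnote would not by itself schedule.

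On dexamethasone, the documents tie no outcome to 4 versus 8 mg. Taken alone it is the smaller of the two matters.

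**Conclusion.** Both inconsistencies are in the current text. The printed schedule shows at most 2 of the 12 chemistry checks that Section 7 requires in cycles 1 and 2, leaving 10 off it, 5 per cycle. The count assumes all six doses are given in each cycle. Four cycle 1 dexamethasone doses carry incompatible instructions, a 16 mg difference for a patient who escalates on day 8 and stays at 56 mg/m². The first is an omission from the schedule of a binding safety requirement; the second is a true conflict in a dosing instruction, and nothing says which text prevails. Neither touches the sample size, the decision rule or the primary endpoint. They should be corrected because they bear on the safety of early doses and the correction needs only wording.

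**What to change.** **Chemistry.** Add a footnote to the CMP row of both calendars: during cycles 1 and 2, chemistry with creatinine is drawn and reviewed before dosing on days 1, 2, 8, 9, 15 and 16, as Section 7 requires. State whether the screening sample may count as the cycle 1 day 1 check. Refer to the footnote in the synopsis and in Sections 3.1 and 6.3. In the same amendment the medical lead could settle the 15 versus 30 mL/min hold and say whether LDH, uric acid and phosphate belong in the pre-dose panel.

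**Dexamethasone.** The medical lead should choose one dose for 56 mg/m² and state it identically in Section 6.1, both calendar footnotes and the two Section 7 statements. A reasonable default for confirmation is the Section 6.1 rule, which changes only the two Section 7 statements. Keeping 4 mg instead changes Section 6.1 and the two footnotes.

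**Cost.** Amendment wording only. Up to 10 chemistry samples per patient would appear on the schedule. Section 7 already requires all of them, all fall on existing infusion visits, and four can share a CBC draw. The dexamethasone change edits two or three sentences.
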